We believe staffing levels are sufficient given the total recruitment target of 10 individuals with SCI and the tasks to be accomplished during the two-year study.

e) Access to target population.

Explain and justify whether you will have access to a population that will allow recruitment of the required number of participants.

We expect to enroll a total of 10 participants with SCI; five individuals in a standard-of-care control group and five individuals in an FES-rowing group. Approximately 35 new patients with SCI are seen per year at the VA Palo Alto Spinal Cord Injury Center. If recruitment from VA Palo Alto proves to be insufficient, we will contact [name] who is the Chief of Spinal Cord Injury, Department of Physical Medicine & Rehabilitation, at the Santa Clara Valley (SCV) Medical Center In San Jose. [name] has agreed to provide consulting assistance as needed on the recruitment of potential participants with spinal cord injuries receiving their medical care at the SCV Medical Center. Approximately 125 new patients with SCI are seen per year at the SCI Rehabilitation Center at SCV Medical Center. Between VAPAHCS and SCV Medical Center, we do not anticipate difficulty in achieving our recruitment target.

f) Access to resources if needed as a consequence of the research.

State whether you have medical or psychological resources available that participants might require as a consequence of the research when applicable. Please describe these resources.

The VA SCI Center provides comprehensive care to patient with SCI on an in- and out-patient basis. There are dedicated physicians, nurses, therapists, and psychologists on staff with extensive experience addressing the medical and mental needs of this patient population. While it is unlikely that there will be research-related events that will require significant medical follow-up, these services are readily available within the facility.

g) Lead Investigator or Coordinating Institution in Multi-site Study.

Please explain (i) your role in coordinating the studies, (ii) procedures for routine communication with other sites, (iii) documentation of routine communications with other sites, (iv) planned management of communication of adverse outcomes, unexpected problems involving risk to participants or others, protocol modifications or interim findings.

1. Purpose

a) In layperson's language state the purpose of the study in 3-5 sentences.

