Following a complete spinal cord injury (SCI), individuals experience progressive bone loss, especially in the legs, with up to 70% of persons with SCI sustaining a fracture at some point during their lifetime. Fractures following SCI are costly to treat and more than half of patients experience a medical complication, requiring extended hospitalization, resulting

Title : Skeletal Health in the Lower Limbs Following Spinal Cord Injury
Approval Period: 01/13/2015 - 09/02/2015

in a substantial impact on their quality of life. To reduce the incidence of fractures, more effective rehabilitation strategies to prevent bone loss are needed. The goal of this research is to determine if bone health can be preserved using an indoor rowing exercise program in which the leg muscles are electrically stimulated using several, small surface electrode pads that are placed on the skin on the front and back thigh muscles. An encouraging case study has recently shown remarkable bone preservation in one individual with SCI who participated in an electrical stimulation rowing program, however, whether other individuals with SCI can achieve the same benefit is currently unknown.

b) State what the Investigator(s) hope to learn from the study. Include an assessment of the importance of this new knowledge.

We hope to learn if participation in a 36-week exercise program consisting of Functional Electrical Stimulation (FES) leg muscle conditioning followed by FES-rowing can significantly attenuate bone loss in the lower limbs in individuals with acute and sub-acute SCI. Reports in the literature of attempts to prevent bone loss following SCI, via the use of anti-osteoporosis drugs, or with static loading in a standing frame, or with dynamic loading from FES-cycling have produced disappointing clinical results. If we are able to show better bone preservation than has been reported previously in a pilot group of five individuals participating in an FES-rowing program, our study will be considered a seminal and clinically important achievement.

c) Explain why human subjects must be used for this project. (i.e. purpose of study is to test efficacy of investigational device in individuals with specific condition; purpose of study is to examine specific behavioral traits in humans in classroom or other environment)

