The objective of this study is to determine if participation in an FES-rowing exercise program can better preserve bone density in the lower limbs of individuals with spinal cord injury than have others types of activities or rehabilitation strategies. Previous literature studies using animals and computer models suggest that the repetitive mechanical stimulation derived from regular participation in a FES-rowing program may be sufficient to attenuate bone loss following SCI. No further animal studies or computer models can confirm the actual benefit in humans, therefore there is no other way to obtain this information without using human subjects.

2. Study Procedures

a) Please SUMMARIZE the research procedures, screening through closeout, which the human subject will undergo. Refer to sections in the protocol attached in section 16, BUT do not copy the clinical protocol. Be clear on what is to be done for research and what is part of standard of care.

In this study we expect to enroll a total of 10 participants with SCI. Five participants will be assigned to a Standard-of-Care (control) group and five participants will be assigned to an FES-rowing intervention group. Group assignment will be partly based on the preference of each potential participant and their willingness to make the necessary time commitment required for participation in a given group, with the added goal, to the extent possible, of matching the two groups for age, gender and time since injury. Only those individuals who have a strong desire to participate in a regular exercise program and who express a willingness to travel to VA Palo Alto the necessary number of times per week to perform FES-rowing will be potential candidates for inclusion in the rowing group.

Bone density measurements for both the Standard-of-Care group and the FES-rowing group will be performed using Dual energy X-ray Absorptiometry (DXA) and peripheral Quantitative Computed Tomography (pQCT). The Standard-of-Care group will undergo no other research procedures.

Title : Skeletal Health in the Lower Limbs Following Spinal Cord Injury
Approval Period: 01/13/2015 - 09/02/2015

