- g) **Study Endpoint. What are the guidelines or end points by which you can evaluate the different treatments (i.e. study drug, device, procedure) during the study? If one proves to be clearly more effective than another (or others) during the course of a study, will the study be terminated before the projected total participant population has been enrolled? When will the study end if no important differences are detected?**

The goal of this pilot study is to obtain preliminary data for five subjects participating in a 36-week FES-rowing group. Because of the small number of subjects, it is important to acquire data for all subjects and for all time points in order to determine the best estimates for key descriptive statistics including the mean, standard deviation and range of bone density changes. The study will not end until five subjects have completed the 36-week FES-rowing program.

3. Background

- a) **Describe past experimental and/or clinical findings leading to the formulation of the study.**

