The identification of potential participants from VA Palo Alto will be facilitated by [name], who is an Attending Physician in the Spinal Cord Injury Service at VA Palo Alto, and by [name], who is the Director of Clinical Research in the VA Palo Alto Spinal Cord Injury Center. In the course of performing their standard clinical responsibilities, both [name] and [name] are in regular contact with inpatients and outpatients in the VA SCI Center. Clinical colleagues of Drs. [name] and [name] whom we will tell about our planned study, will also assist in identifying potential subjects during the course of their standard clinical interactions with patients. A similar situation exists for [name] who is the Chief of Spinal Cord Injury at the Santa Clara Valley Medical Center in San Jose. Any patients who appear to be possible candidates for the study will be told briefly about the study by Drs. [name] and [name], or by their clinical colleagues, and if a patient expresses an interest in the study, they will be given contact information for [name]. Interested patients will be able to ask any additional questions by contacting [name].

- h) Inclusion and Exclusion Criteria.
Identify inclusion criteria.**

Subjects in the rowing groups:
· male and female SCI outpatients or inpatients
· have a T1 to T12, ASIA-A or ASIA-B, spinal cord injury
· be at least 18 year old

Title : Skeletal Health in the Lower Limbs Following Spinal Cord Injury
Approval Period: 01/13/2015 - 09/02/2015

- have their physician's clearance to exercise
- between 3 and 12 months post spinal cord injury
- minimum passive hip flexion range of motion (ROM) from 20 to 100 deg
- minimum passive knee flexion ROM from 20 to 100 deg
- minimum passive ankle ROM from +10 deg (dorsi-flexion) to -15 deg (plantar-flexion)
- currently use a manual wheelchair
- be able to perform independent and safe transfers to and from their wheelchair

Subjects in the control group:

- male and female SCI outpatients or inpatients
- have a C5 to T12, ASIA-A or ASIA-B, spinal cord injury
- be at least 18 year old
- between 3 and 12 months post spinal cord injury
- be able to perform safe transfers to and from their wheelchair, either independently or with assistance

Identify exclusion criteria.

Exclusion Criteria

- pregnant women
- women of childbearing potential not practicing a reliable method of contraception
- women who are post-menopausal
- have mechanical instability of the spine

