- resting blood pressure higher than 140/90
- a grade 1 or greater, sacral, gluteal or ischial pressure ulcer
- history of low trauma, lower limb fracture since SCI
- renal disease
- current osteomyelitis
- current thrombosis/hemorrhage
- cancer
- other neurological disease (i.e. stroke, peripheral neuropathy, myopathy)
- any implanted electronic device
- active treatment for epilepsy
- regular use of tobacco
- known coronary artery disease
- family history of sudden cardiac death
- current use of cardioactive medications, e.g., for treatment of congestive heart failure or arrhythmia
- current use of medications that can affect bone density and fracture risk including:
 - bisphosphonates
 - parathyroid hormone (PTH) and PTH analogs
 - androgenic steroids
 - estrogenic steroids
 - glucocorticoids
 - anti-epileptics

We will also exclude patients with cognitive impairments that will limit understanding of the nature of the project or understanding of the informed consent process.

- i) **Describe your screening procedures, including how qualifying laboratory values will be obtained. If you are collecting personal health information prior to enrollment (e.g., telephone screening), please request a waiver of authorization for recruitment (in section 15).**

Subjects initially identified as potential candidates by Drs. [name] and [name] or their clinical colleagues at VA Palo Alto or Santa Clara Valley Medical Center, will be given contact information for [name]. Interested patients will be told to contact [name] to find out about the study and ask any additional questions.

- j) **Describe how you will be cognizant of other protocols in which participants might be enrolled. Please explain if participants will be enrolled in more than one study.**

Title : Skeletal Health in the Lower Limbs Following Spinal Cord Injury
Approval Period: 01/13/2015 - 09/02/2015

Patients will be asked during recruitment if they are participating in any other studies. Participants will not be eligible for our study if they are already participating in another research study that uses drugs or exercise to maintain skeletal health.

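### Bone-active drugs are excluded only while in current use, so a bisphosphonate given after the injury and stopped before screening is neither excluded nor recorded

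*Combined protocol and SAP*

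**What the plan says.** Section 8(h) lists among its exclusions "current use of medications that can affect bone density and fracture risk including" bisphosphonates, parathyroid hormone and its analogs, androgenic and estrogenic steroids, glucocorticoids and anti-epileptics. It gives no washout or look-back and does not define current.

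The same list does look back for another item: it excludes a "history of low trauma, lower limb fracture since SCI".

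Both groups must be "between 3 and 12 months post spinal cord injury" at entry. The rule on other studies, in section 8(j), bars only people who are in another skeletal-health study at the time. A person who has finished one is not barred.

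The resources section, under access to the target population, plans "five individuals in a standard-of-care control group and five individuals in an FES-rowing group". Section 2(a) states that "Group assignment will be partly based on the preference of each potential participant", with matching as far as possible on age, gender and time since injury. Section 2(g) gives the summary as "key descriptive statistics including the mean, standard deviation and range of bone density changes".

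Section 1(b) mentions "attempts to prevent bone loss following SCI, via the use of anti-osteoporosis drugs". It groups these with standing-frame loading and FES-cycling and calls the clinical results disappointing.

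**The concern.** The exclusion exists because the listed drugs can change the quantity that the trial measures. It stops at the day of screening, although patients enter up to 12 months after injury and section 1(b) says that such drugs have been tried against this very bone loss. A person treated soon after injury and since stopped passes the criterion.

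If part of the drug's effect remained over the 36 weeks, bone loss would be smaller for a reason unrelated to rowing. In a rower this would flatter both comparisons that the protocol makes: rowers against controls, and rowers against earlier reports. In a control it would make the control group lose less bone and so hide a rowing benefit. Allocation is not randomised and each group has five people, so chance balance cannot be relied on, and prior drug use is not a matching factor.

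**Working it through.** The documents give no standard deviation, effect size or sample-size calculation, so there is no figure of the plan's own to reproduce. The check is one of wording, followed by an illustration.

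**Wording.**

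- *Is past use excluded anywhere?* The places that could do it are 8(h) (criteria), 8(i) (screening), 8(j) (other studies), 9(a) and 9(c) (risks and their control), 9(d) (withdrawal) and 15.1 (phone assessment). None excludes past use of a bone-active drug or sets a washout.
- *Is it recorded?* Section 11(b) lists identifiers, injury history, date of injury and images. It does not mention medication history. That is a privacy section and not a data-collection form, but no other supplied section adds medication history.
- *Is it handled by design or analysis?* The matching factors in 2(a) do not include it, and 2(g) has no breakdown by exposure.
- *Is there time for it to occur?* Yes. At entry, 3 to 12 months have passed since injury.

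**Size, on assumed inputs.** Let e be the residual effect, in percentage points of bone density change over 36 weeks, and k the number exposed in a group of five. The group mean moves by k × e / 5.

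| Assumed e | k = 1 | k = 2 |
|---|---|---|
| 2 | 2/5 = 0.4 | 4/5 = 0.8 |
| 5 | 5/5 = 1.0 | 10/5 = 2.0 |
| 10 | 10/5 = 2.0 | 20/5 = 4.0 |

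**How often, on assumed inputs.** Let p be the share of otherwise eligible patients with past exposure, taken as the same in both groups and independent between people. The chance that at least one of five rowers is exposed is 1 − (1 − p)^5. The chance that the two groups have unequal numbers exposed is 1 − Σ [C(5,x) p^x (1 − p)^(5−x)]², summed over x = 0 to 5.

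| Assumed p | At least one of five rowers | Unequal numbers, 5 v 5 |
|---|---|---|
| 5% | 23% | 36% |
| 10% | 41% | 54% |
| 20% | 67% | 68% |
| 30% | 83% | 73% |

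For example, at p = 10%, 1 − 0.9^5 = 1 − 0.590 = 0.41. Both e and p are placeholders, because the documents inform neither.

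**The case against.** The other side has five arguments.

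- **The documents point to a small drug effect.** The disappointing results noted in 1(b) are their only statement on drug effect after spinal cord injury. This stands and is a reason not to assume a large e. It does not close the gap, because 8(h) itself treats these drugs as able to affect bone density.
- **Persistence after stopping is not in the documents.** This also stands. A reader might infer that residual drug effect will pass for bone preservation. The documents support only the weaker statement that the criterion leaves the possibility open. Nor do they support extending the argument to parathyroid hormone analogs or the other listed classes, and no such claim is made here.
- **Staff could read current use broadly**, and the VA proposal and phone script listed in section 16 were not supplied and may say more. Both are possible. The text does not require the broad reading.
- **The range would expose an outlier.** In part. An atypical person among five might be visible, but without an exposure record the reason would not be.
- **This is a small descriptive pilot with larger threats to comparability**, such as preference-based assignment and different permitted injury levels (T1–T12 for rowers, C5–T12 for controls). True, and it limits the priority. Those features are part of the design, whereas this gap can be closed with one line.

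A reader might also attach a separate figure for inflation of the standard deviation. That would depend on the spread among the other participants, which the documents do not give. With underlying SD s, the expected variance with one of five exposed is s² + 0.2e². For an assumed s = 5, e = 2 gives √25.8 = 5.1 and e = 10 gives √45 = 6.7, so the rise can be slight.

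**Conclusion.** The gap in eligibility and recording is real on the supplied text: post-injury bisphosphonate use that ended before screening is not excluded, recorded or accounted for. The bias is conditional. It requires that at least one such person enrols and that some effect outlasts dosing, and the documents settle neither. If both hold, the shift in a group mean is one fifth of the residual effect per exposed person, and its direction depends on the group that the person is in. It is a possible confounder that is cheap to remove, and not a demonstrated bias. It should be fixed, at moderate priority.

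**What to change.** 1. In 8(h), for bisphosphonates, replace the current-use wording with use since the spinal cord injury. This matches the anchor already used for fractures. Given the entry window it looks back 3 to 12 months, so adding a 12-month clause would mainly bring in pre-injury use. Whether to look back further than the injury is for the sponsor to decide.
2. Define current use for the remaining drug classes.
3. Ask about prior use in the phone call that already assesses eligibility (15.1), and record at baseline all bone-active drug use since injury, for every class in the list.
4. In 2(g), add that group summaries will be shown with and without any exposed participant. This covers anyone enrolled before the change and anyone exposed to another listed class.

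The cost is one IRB amendment, one screening question and one baseline item. Possibly a few candidates would be lost. The number cannot be estimated, because the roughly 35 new patients a year at the VA centre, and 125 at the second centre if it is needed, are all new spinal cord injury patients and not only those who meet the other criteria.
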